3.1. Analysis Sets

Analysis sets define the subjects to be included in an analysis. Analysis sets and their definitions are provided in this section. The analysis set will be identified and included as a subtitle of each table, figure, and listing.

For each analysis set, the number and percentage of subjects eligible for inclusion will be summarized by treatment group, phase, and dose level, treatment arm, or cohort if applicable, as elaborated in [Table 3-2](#) in Section 3.2.

A listing of reasons for exclusion from analysis sets will be provided by subject.

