3.1.3. Full Analysis Set

The Full Analysis Set (FAS) includes all subjects who received at least 1 dose of study drug with treatment designated according to the planned treatment.

This analysis set will be used in the analyses of subject characteristics and efficacy.

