3.2. Subject Grouping

For analyses based on the FAS, subjects will be grouped according to the treatment to which they were assigned or randomized:

- For the dose escalation of each treatment group, subjects will be grouped according to the ENTO dose level first received.
- For all dose expansion cohorts, all the subjects were assigned to a dose level of 400 mg.
- For Group B Phase 2 randomization, subjects will be grouped according to the treatment to which they were randomized.

For analyses based on the Safety Analysis Set and the PK Analysis Set, subjects will be grouped according to the actual treatment received. The actual treatment received will differ from the assigned/randomized treatment only when their actual treatment differs from assigned/randomized treatment for the entire treatment duration.

As all treated subjects in this study received the assigned/randomized treatment, the FAS will be the same as the Safety Analysis Set for all treatment groups/cohort.

Table 3-2 shows the column headers of the summary tables for all treatment groups/cohort. Column “Total” is not applicable to the efficacy summary tables for Group B Phase 2 randomization and Group C Phase 2.

Table 3-2. Column Headers of the Summary Tables

Treatment Group/Cohort	Column Header			
Group A Phase 1b	Dose Level 0 200 mg BID	Dose Level 1 400 mg BID	Total	
Group A Phase 2	Dose Level 1 400 mg BID			
Group A (Phase 1b + Phase 2)	Dose Level 0 200 mg BID	Dose Level 1 400 mg BID	Total	
Group B Phase 1b	Dose Level 0 200 mg BID	Dose Level 1 400 mg BID	Total	
Group B Phase 2 Safety Run-in	Dose Level 1 400 mg BID			
Group B Phase 2 Randomization	ENTO (400 mg) + Decitabine	ENTO (400 mg) + Azacitidine	Total	
Group C Phase 1b	Dose Level 0 400 mg BID	Dose Level 1 800 mg BID	Total	
Group C Phase 2	Cohort C1A ENTO (400 mg BID)	Cohort C2 ENTO (400 mg BID)	Cohort C3 ENTO (400 mg BID)	Total
Group C (Phase 1b + Phase 2)	Dose Level 0 400 mg BID	Dose Level 1 800 mg BID	Total	

In addition, in Group C, Phase 1b subjects who meet the following criteria will be pooled with Phase 2 Cohort C1A or Cohort C3 as described in Section 1.2:

- Pooled analysis (1): Group C Phase 1b subjects who were R/R AML and received at least 21 days of ENTO (400 mg or 800 mg) and Group C Phase 2 Cohort C1A (400 mg) will be pooled to provide an adequate sample size for futility analysis for subjects with R/R AML.

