- Pooled analysis (2): Group C Phase 1b subjects who were previously untreated AML, unfit for Group A or B, and received at least 21 days of ENTO (400 mg or 800 mg), and Group C Phase 2 Cohort C3 will be pooled to provide an adequate sample size for efficacy analyses for subjects with previously untreated AML and unfit for Group A or B.

Only efficacy analyses will be done for the pooled Group C cohorts. Summary will be based on FAS.

Table 3-3 presents the titles and column headers of the summary tables for the pooled analyses of Group C.

Table 3-3. Pooled Analyses of Group C

Pooled Analysis	Title	Column Header		
(1)	Pooled Analysis of Group C Phase 1b and Phase 2 of Cohort C1A (All Doses) in R/R AML	Dose Level 0 400 mg BID	Dose Level 1 800 mg BID	Total
(2)	Pooled Analysis of Group C Phase 1b and Phase 2 of Cohort C3 (All Doses) in Untreated AML	Dose Level 0 400 mg BID	Dose Level 1 800 mg BID	Total

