The category “Other” includes 2 subcategories: Treatment Failure [TF] and No Assessment Done. All subjects in “Other” will be considered as nonresponders and will be included in the denominator when calculating the remission rates per best overall response.

As a sensitivity analysis, complete remission rate, composite complete remission (CR/CRi) rate, and overall response (CR/CRi/PR) rate per best overall response ever achieved during the treatment will be summarized for Groups A and B. The category “Other” includes 3 subcategories: Treatment Failure [TF], Early Treatment Assessment [ETA], and No Assessment Done. For subjects who had response assessment but didn’t achieve any of the first 5 categories

listed above as the best overall response, TF will be the best overall response for those who received 2 induction cycles in Group A or received ≥ 2 induction cycles in Group B, and ETA will be the best overall response for those who only received ≤ 1 induction cycle. All subjects in “Other” will be considered as nonresponders and will be included in the denominator when calculating the remission rates per best overall response.

As an example, assuming a subject in Group A received two induction cycles and discontinued all study drugs, if subject achieved PR at end of Cycle 1 but relapsed at end of Cycle 2, the best overall response is PR while the response assessment at induction completion is relapse.

When the date of initiation of SCT/anticancer therapy other than the study treatment is incomplete or missing, the following algorithm will be followed:

- If the day is missing but the month and year are available, then the imputed day will be the last day of the month.
- If day and month are missing but year is available, then the imputed day and month will be 01Jan or the last day of the month for the last adequate disease assessment if they have the same year, whichever is later.

The following subgroup analyses will be provided for primary analysis:

- Age (<60 years, ≥ 60 years; applicable to Groups A and C)
- Age (≤ 75 years, >75 years; applicable to Group B)
- ELN risk group (Favorable, Intermediate -I, Intermediate -II, Adverse)
- De novo and Secondary AML
- Age and ELN risk group (applicable to Group A)
- With and without MLL
- FLT3-ITD mutation (applicable to Groups A and B)
- NPM1 mutation (applicable to Groups A and B)

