
No postbaseline assessment, no death
	
Censored
	
Date of first dose

No treatment failure/relapse/death
	
Censored
	
Date of last response assessment (and prior to other anti-cancer therapy if any) or first dosing date, whichever is later

Other anti-cancer therapy started prior to treatment failure/relapse/death	Censored	Date of last response assessment prior to other anti-cancer therapy or first dosing date, whichever is later
Days from last response assessment prior to treatment failure/relapse/death or first dosing date, whichever is later, to treatment failure/relapse/death was not within the window defined above	Censored	Date of last response assessment prior to treatment failure/relapse/death or first dosing date, whichever is later

Censoring Rules for OS:

- For a subject who is not known to have died by the end of study follow-up, OS is censored on the date the subject was last known to be alive.

For EFS or OS in months, the calculation is based on the following formula:

$$(\text{date of event/censoring} - \text{date of first dose} + 1) / 30.4375.$$

EFS and OS will be analyzed using Kaplan-Meier (KM) methods. The KM estimate of the survival function will be computed and the results will be presented using KM curves. The median will be provided along with the corresponding 95% CI. Additionally, the 25% and 75% percentiles for these endpoints will also be provided.

Follow up time for OS will be summarized as continuous variable with descriptive statistics.

- For a subject who is not known to have died by the end of study follow-up, duration of OS follow up in months = $(\text{date of last known to be alive} - \text{date of first dose} + 1) / 30.4375$
- For the remaining subjects, duration of OS follow up in months = $(\text{date of follow-up cutoff} - \text{date of first dose} + 1) / 30.4375$

Data listing for EFS and OS will be presented.

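### The pooled Group C efficacy tables leave out Phase 1b subjects with under 21 days of ENTO, keep such subjects from C1A and C3, and are labelled FAS

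*SAP*

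**What the plan says.** SAP 3.2 (repeated in SAP 1.2 and 1.3) defines the Phase 1b part of the relapsed/refractory pool as "Group C Phase 1b subjects who were R/R AML and received at least 21 days of ENTO (400 mg or 800 mg", and adds Cohort C1A. The untreated pool has the same 21-day minimum for Phase 1b and adds Cohort C3. Neither C1A nor C3 has a minimum exposure.

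On the analysis set, SAP 3.2 says: "Only efficacy analyses will be done for the pooled Group C cohorts. Summary will be based on FAS". SAP 3.1.3 says the FAS "includes all subjects who received at least 1 dose of study drug with treatment designated according to the planned treatment". SAP 3.1 says: "The analysis set will be identified and included as a subtitle of each table, figure, and listing". The Table 3-3 title for the first pool is "Pooled Analysis of Group C Phase 1b and Phase 2 of Cohort C1A (All Doses) in R/R AML"; the title for the second is built the same way. Neither mentions 21 days.

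For Group C response, SAP 6.1.2 says that subjects with treatment failure or no assessment "will be considered as nonresponders and will be included in the denominator when calculating the remission rates per best overall response". SAP 6 runs response, EFS, OS and the exploratory efficacy endpoints on both pools, by dose level and in total. On dose, SAP 3.2 says: "For all dose expansion cohorts, all the subjects were assigned to a dose level of 400 mg".

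**The concern.** Twenty-one days of treatment is known only after treatment starts, and it is related to outcome: a subject who dies, progresses or stops early cannot meet it. Applying it to one part of a pool removes such subjects from that part only. It also departs from the SAP's own rule that subjects without a response or an assessment count as nonresponders.

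The gap was foreseeable. The same 21-day threshold governs DLT evaluability (protocol 3.2, SAP 3.1.5), and the protocol replaces subjects who miss it for reasons other than DLT. The plan therefore expected that some treated subjects might fall below it. Protocol 8.2.1 uses the FAS for efficacy and, unless stated otherwise, pools the phases by dose level first received, with no exposure minimum. SAP 6.5 does not list the restriction among its changes from the protocol.

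These are the only planned tables that combine the two phases by disease status, and the SAP relies on them for adequate sample size. A reader who sees an FAS subtitle will take it that every treated subject is counted. The dose columns also differ in kind: all expansion subjects were at 400 mg, so the 800 mg column holds only filtered subjects and the 400 mg column is mixed.

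**Working it through.** **1. The plan's own figure.** SAP 1.3 gives an 84% chance of stopping at a true CR/CRi rate of 20% and 22% at 40%, stopping if fewer than 5 of 15 respond. Exact binomial: P(X ≤ 4 | n = 15, p = 0.20) = 0.836 and P(X ≤ 4 | n = 15, p = 0.40) = 0.217. Both are reproduced. They assume one common response rate in all 15 subjects, 9 of whom are filtered.

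**2. How many could be missing.** SAP 1.2 has 9 relapsed/refractory and 3 untreated Phase 1b subjects passing: 9 + 3 = 12. SAP 1.3 caps Phase 1b at 14 per group (12 evaluable plus 10% unevaluable: 12/0.9 = 13.3, rounded up). If the cap held, at most 14 − 12 = 2 are excluded across both pools. The number actually excluded is not given.

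**3. The same course in the two parts of a pool** (a subject with under 21 days of ENTO).
- Early death: a C1A or C3 subject is an OS event, and an EFS event if Table 6-1's conditions are met. A Phase 1b subject is absent. Pooled OS is biased upward.
- Non-response assessment, alive: a C1A or C3 subject is a nonresponder and, within the Table 6-1 window, an EFS treatment failure. A Phase 1b subject is absent. EFS is biased upward.
- "No postbaseline assessment, no death": this Table 6-1 row censors EFS at first dose, so omitting the subject does not move the EFS estimate. The subject would still count as a nonresponder.
- Other anti-cancer therapy before any EFS event: EFS is censored, so again no such bias.

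**4. Size for response.** Assumption: k = 0, 1 or 2 excluded nonresponders, all in one pool. Base n = 15 suits either pool: 9 + 6 = 15 relapsed/refractory, or 3 + 12 = 15 untreated, since the protocol synopsis closes C3 at 12. The rate goes from r/15 to r/(15 + k), with Clopper-Pearson 95% limits.

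| | k = 0 | k = 1 | k = 2 |
|---|---|---|---|
| r = 0 | 0% (upper 21.8%) | 0% (upper 20.6%) | 0% (upper 19.5%) |
| r = 3 (illustrative) | 20.0% (4.3–48.1) | 18.8% (4.0–45.6) | 17.6% (3.8–43.4) |

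SAP 1 cites a lack of responses to monotherapy, so the first row may be the closer one.

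**5. Size for survival.** Assumption: those excluded died before Day 21 and everyone else was alive then. The pooled OS curve at Day 21 would be 15/16 = 94% or 15/17 = 88%, against 100% in the filtered pool. The SAP does not tabulate this time point; it would show on the Kaplan-Meier curve.

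**6. Direction for futility.** Assumption: a share q of Phase 1b subjects never reach 21 days and never respond, so those who pass respond at p/(1 − q). Combining 9 filtered and 6 unfiltered subjects, the stopping probabilities at true rates of 20% and 40% are 0.800 and 0.161 for q = 0.10, and 0.751 and 0.104 for q = 0.20. The filter makes stopping less likely. Adding nonresponders cannot turn fewer than 5 responders into 5.

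**The case against.** The strongest reply is that excluded subjects are not lost to the report. SAP 6 presents efficacy for every row of Table 3-2, and the rows for Group C Phase 1b and for Group C Phase 1b plus Phase 2 have no 21-day filter. That stands, and it also provides an unfiltered comparison of 400 mg with 800 mg. Because Phase 1b admits only relapsed/refractory or previously untreated subjects (protocol 4.2), the total excluded follows by subtraction: the Phase 1b N, minus the first pool's N less C1A, minus the second pool's N less C3. SAP 4.1 also lists the IDs of pooled subjects. What these tables do not do is split Phase 1b by disease status, which is the purpose of the pools. The reasons-for-exclusion listing in SAP 3.1 covers the analysis sets, and the 21-day pool is not one of them.

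It can also be said that every pooled subject belongs to the FAS and that the SAP text states the condition openly. Both are true, but the reader of the table sees neither fact. The analyses are descriptive, the cohorts are closed and no decision hangs on the result. That limits the weight of the point without removing it.

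A reader might infer that early failures were in fact removed. The documents do not show that anyone was excluded, and a subject can fall short through toxicity or withdrawal. Nor can the effect in the 800 mg column be sized: the split by dose and disease status is not given, and the untreated pool has only 3 Phase 1b subjects over both doses.

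**Conclusion.** The point holds as a conditional one. A stated rule filters one part of each pool on post-baseline exposure, and the label and titles hide it. If any treated Phase 1b subject fell short, pooled OS is biased upward where early deaths are removed. EFS is biased upward where the subject would have had an event. Response is biased upward where there are responders and the excluded subject was not one of them.

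The effect is zero if nobody fell short. It involves at most two subjects across both pools if the cap of 14 held and the SAP's count of 12 is right. With no responders, only the upper confidence limit for response changes; survival is the more exposed endpoint.

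A reader might infer that the C1A futility decision is undermined. It is not: the filter works against stopping, and futility was met regardless. The point should be fixed because the remedy is cheap and the tables would otherwise be misread.

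**What to change.** Run the main pooled efficacy tables on all treated (FAS) Group C Phase 1b subjects of matching disease status, together with C1A or C3. Handle those under 21 days by the SAP's existing rules for response (6.1.2) and for EFS and OS (6.2.2). Keep the 21-day relapsed/refractory version as the record of the futility analysis, noting that the 84% and 22% assume 15 unselected subjects. Keep the 21-day versions of both pools as sensitivity analyses, with the condition in the table title. Report the number excluded per pool and dose level, with reasons.

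The cost is SAP wording and two re-run pooled analyses, with no new data. Rates may be slightly lower, and the pooled N may differ from the planned figure.

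Two counts need reconciling as separate points. Protocol 3.1.6 gives C1A as 15, while the SAP has 6 in C1A plus 9 from Phase 1b. Protocol 1.3.1 gives 9 Group C escalation subjects as of August 2017, while the SAP has 9 + 3 = 12 with at least 21 days.

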3.3. Strata and Covariates

In Group B Phase 2 randomization, approximately 40 subjects were planned to be randomly assigned to treatment arm ENTO + decitabine or ENTO + azacitidine via the interactive web response system (IWRS) in a 1:1 ratio using a stratified randomization schedule. Stratification will be based on the following variables:

- Age: ≤ 75 years vs > 75 years
- WBC: $\leq 5,000/uL$ vs $> 5,000/uL$

Here age will be calculated as (date of randomization – date of birth+1) / 365.25. Subject with age at randomization ≤ 75 years or > 75 years will be assigned to “Age ≤ 75 years” or “Age > 75 years” respectively.

If there are discrepancies in the value used for stratification assignment between the IWRS and the clinical database, the value collected in the clinical database will be used for the summary.

No covariates will be included in the efficacy analyses.

3.4. Examination of Subject Subgroups

Primary efficacy endpoints will be examined in the following subgroups:

- Age (applicable to Groups A and C)
 - < 60 years
 - ≥ 60 years

- Age (applicable to Group B)
 - ≤ 75 years
 - > 75 years
- European LeukemiaNet (ELN) Risk Group
 - Favorable
 - Intermediate-I
 - Intermediate-II
 - Adverse
- Age and ELN risk group (applicable to Group A)
- AML Type
 - De novo AML
 - Secondary AML

Note that the CRF didn't collect AML type directly and this will be derived from the AML subtype collected in the CRF Form "Staging". Subject with the WHO classification subtype "AML with myelodysplasia-related changes" will be considered as "Secondary AML". Subjects with other WHO classification subtypes as well as all the French-American-British (FAB) classification subtypes will be considered as "De novo AML". See [Appendix 1](#) for the list of FAS and WHO classification subtypes.

- MLL
 - With MLL
 - Without MLL
- FLT3-ITD Mutation (applicable to Groups A and B)
 - FLT3-ITD+
 - FLT3-ITD-

- NPM1 Mutation (applicable to Groups A and B)
 - NPM1+
 - NPM1-

For Group B Phase 2 randomization cohort, subgrouping of subjects based on randomization stratification factors will be explored for subgroup analyses as well.

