Cohort C3: This cohort is designed to enroll previously untreated AML subjects who are unfit (eg, very elderly, have multiple comorbidities, and a poor ECOG/performance status) for chemotherapy or hypomethylating agent, or refuse either of these 2 treatment options. This amendment identifies enrollment closure of this cohort.

Number of Subjects Planned:	Approximately 190 subjects
Target Population:	Subjects with Acute Myeloid Leukemia
Duration of Treatment:	Subjects may continue receiving ENTO until treatment failure, planned completion of treatment, start of new therapy, unacceptable toxicity, withdrawal of consent by subject, or withdrawal from study by investigator.
Safety Review:	Safety data will be reviewed continuously during the course of the study. The Cancer Therapy Evaluation Program (CTEP) Active Version of the National Cancer Institute (NCI) Common Terminology Criteria for Adverse Events (CTCAE) version 4.03 will be utilized for Adverse Event (AE) reporting.
Main Diagnosis and Disease Eligibility Criteria:	AML (de novo, therapy related [t-AML], or secondary AML) All groups will build on ENTO backbone Group A 
Subjects age \geq 18 years with previously untreated AML by World Health Organization (WHO) criteria, excluding acute promyelocytic leukemia (M3), who are able and should receive up to 2 cycles of induction chemotherapy with 7+3 as determined by the treating physician

Group B

- Subjects age > 70 years with previously untreated AML by WHO criteria, excluding acute promyelocytic leukemia (M3)
- Subjects age ≤ 70 years with previously untreated AML by WHO criteria, excluding acute promyelocytic leukemia (M3), who refuse or are unable to receive 7+3 as determined by the treating physician

Group C Phase 1b (Dose Escalation)

- Subjects age ≥ 18 years with relapsed/refractory AML by WHO criteria, excluding acute promyelocytic leukemia (M3)
- Subjects with previously untreated AML by WHO criteria, excluding acute promyelocytic leukemia (M3), and who would have met disease eligibility criteria for Group A or B but refuse or are unable to receive 7+3 or decitabine chemotherapy as determined by the treating physician

Group C Phase 2 (Dose Expansion)

- Cohort C1A: Subjects age ≥ 18 years with relapsed or refractory AML by WHO criteria, excluding acute promyelocytic leukemia (M3)
- Cohort C2: Subjects age ≥ 18 years with relapsed/refractory AML with MLL

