4.3. Exclusion Criteria

Subjects who meet any of the following exclusion criteria are not eligible for study participation:

- 1) Subjects with acute promyelocytic leukemia (M3)
- 2) Known active central nervous system or leptomeningeal leukemic involvement.
Note: Central nervous system testing (CSF analysis) is only required in subjects with suspected involvement based on symptoms or signs.
- 3) Treatment with proton pump inhibitors (PPIs) within 7 days prior to enrollment. Note: PPIs are likely to interfere with ENTO absorption, thus requiring a 7-day washout period. H2 blockers and antacids will be allowed for use during the protocol.
- 4) History of active non-myeloid malignancy except for the following: adequately treated local basal cell or squamous cell carcinoma of the skin, cervical carcinoma in situ, superficial bladder cancer, asymptomatic prostate cancer without known metastatic disease and with no requirement for therapy or requiring only hormonal therapy and with normal prostate specific antigen for > 1 year prior to start of study therapy, or any other cancer that has been in complete remission without treatment for ≥ 5 years prior to enrollment. Subjects who are on prophylaxis with long-term adjuvant hormonal therapy and are ≥ 5 years from therapy for their primary tumor are eligible for enrollment.
- 5) Evidence of ongoing uncontrolled systemic bacterial, fungal, or viral infection at the time of start of study treatment. Note: Subjects with localized fungal infections of skin or nails are eligible.
- 6) Ongoing, drug-induced liver injury, known chronic active hepatitis C Virus (HCV), chronic active hepatitis B Virus (HBV), alcoholic liver disease, non-alcoholic steatohepatitis, primary biliary cirrhosis, ongoing extrahepatic obstruction caused by cholelithiasis, cirrhosis of the liver, or portal hypertension

- 7) Ongoing (within the past 6 weeks) hepatic encephalopathy
- 8) Ongoing drug-induced pneumonitis
- 9) Ongoing inflammatory bowel disease
- 10) Ongoing alcohol or drug addiction as determined by investigator
- 11) Pregnancy or breastfeeding
- 12) History of prior allogeneic bone marrow progenitor cell or solid organ transplantation.
Note: prior allogeneic bone marrow progenitor cell or solid organ transplantation is NOT an exclusion criteria for Cohort C2 ie, MLL cohort.

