5.2. Other Baseline Characteristics

Other baseline characteristics include body weight (in kg), height (in cm), body mass index (BMI; in kg/m²), bone marrow blasts (in %), ECOG performance status, cytogenetics (normal or abnormal), ELN risk group, de novo/secondary AML, MLL status, and molecular mutation assessment. Bone marrow blasts will be based on the blasts in bone marrow aspirate. If blasts in bone marrow aspirate are not available, blasts in bone marrow biopsy will be used. These baseline characteristics will be summarized using descriptive statistics for continuous variables and using number and percentage of subjects for categorical variables.

By-subject listings of other baseline characteristics will be provided.

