5.3. Medical History

Medical history will be collected at screening for disease-specific and general conditions (ie, conditions not specific to the disease being studied).

A summary of disease-specific medical history will be provided. AML classification at screening will be presented by the FAB and the WHO classification subtypes. Subtypes will be summarized using summary statistics for a categorical variable. Time since AML diagnosis (weeks) will be calculated as (date of first dose of study drug – date of diagnosis)/7. Time since AML diagnosis will be summarized by using summary statistics for continuous variables.

General medical history data will not be coded.

By-subject listings of disease-specific and general medical history will be provided.

In deriving the time since AML diagnosis, partial dates of diagnosis will be identified, and the partial dates will be imputed as follows:

- If day and month are missing but year is available, then the imputed day and month will be 01 Jan.
- If day is missing but the month and year are available, then the imputed day will be the first day of the month.
- Partial date will not be imputed if the year is missing.

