For Group B phase 2 randomization, similar analyses will be provided by randomization stratum if there is sufficient sample size in the subgroup. The denominator for the percentage of subjects in the stratum will be the total number of randomized subjects. If there are discrepancies in the value used for stratification assignment between the IWRS and the clinical database, the value collected in the clinical database will be used for the summary.

Data listings for the clinical responses will be presented.

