Appendix 1. List of FAB/WHO Classification Subtypes

FAB Classification	WHO Classification
M0: Undifferentiated acute myeloblastic leukemia	AML with certain genetic abnormalities
M1: Acute myeloblastic leukemia with minimal maturation	AML with myelodysplasia-related changes
M2: Acute myeloblastic leukemia with maturation	AML related to previous chemotherapy or radiation
M3: Acute promyelocytic leukemia (APL)	
 • AML not otherwise specified: • AML with minimal differentiation (M0) • AML without maturation (M1) • AML with maturation (M2) • Acute myelomonocytic leukemia (M4) • Acute monocytic leukemia (M5) • Acute erythroid leukemia (M6) • Acute megakaryoblastic leukemia (M7) • Acute basophilic leukemia • Acute panmyelosis with fibrosis
M4: Acute myelomonocytic leukemia	
M4 eos: Acute myelomonocytic leukemia with eosinophilia	
M5: Acute monocytic leukemia	
M6: Acute erythroid leukemia	
M7: Acute megakaryoblastic leukemia	

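### The SAP's AML-type rule would label therapy-related AML as de novo AML

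*SAP*

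**What the plan says.** SAP Section 3.4 explains that the case report form did not collect AML type directly, so the variable is derived from the recorded subtype. Only the WHO subtype for myelodysplasia-related changes is mapped to secondary AML. Everything else is mapped by default: "Subjects with other WHO classification subtypes as well as all the French-American-British (FAB) classification subtypes will be considered as" de novo AML.

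The same section refers to SAP Appendix 1 for the list of subtypes. In the WHO column there, "AML related to previous chemotherapy or radiation" has its own entry, apart from the myelodysplasia-related one.

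The protocol synopsis, under the main diagnosis and disease eligibility criteria, describes the population as "AML (de novo, therapy related [t-AML], or secondary AML".

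The derived variable is used in two places:

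- SAP Section 6.1.2 includes "De novo and Secondary AML" among the subgroup analyses of the primary efficacy endpoints. Unlike the age, FLT3-ITD and NPM1 subgroups, it is not limited to particular treatment groups.
- SAP Section 5.2 lists it among the baseline characteristics to be summarized: "ELN risk group, de novo/secondary AML, MLL status, and molecular mutation assessment".

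**The concern.** The protocol distinguishes three kinds of eligible AML. The SAP reduces them to two and places the therapy-related kind under de novo, the label from which the protocol separates it. A reader of a table row headed de novo AML would not expect to find cases that arose after chemotherapy or radiation. If any such subject was recorded, the de novo response rates and the baseline count would describe a mixed set under a label that suggests otherwise.

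The stated reason for deriving the variable does not require this mapping. Lack of a direct AML-type field justifies using the subtype. It does not justify the default, because the subtype list already contains the entry that identifies these subjects.

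**Working it through.** **Applying the rule.** The plan gives no figure to reproduce here. The check is to apply the Section 3.4 rule to each entry of SAP Appendix 1.

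| Appendix 1 entry | Label under Section 3.4 |
|---|---|
| WHO: genetically defined AML | De novo |
| WHO: myelodysplasia-related AML | Secondary |
| WHO: "AML related to previous chemotherapy or radiation" | De novo |
| WHO: not otherwise specified, with its sub-entries | De novo |
| FAB: all entries | De novo |

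The third row conflicts with the protocol synopsis. Neither document makes an exception for it.

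**Possible size.** The documents give no count of affected subjects, no response difference and no row sizes, so all three are assumed below.

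Let p be the response rate of the other subjects in the de novo row, f the fraction of the row that is therapy-related, and d the number of points by which their response rate is lower. The row then shows (1 − f) × p + f × (p − d) = p − f × d, so it is off by f × d.

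- f = 0 or d = 0: shift 0
- f = 5%: 0.05 × 20 = 1.0 point; 0.05 × 40 = 2.0 points
- f = 10%: 0.10 × 20 = 2.0 points; 0.10 × 40 = 4.0 points
- f = 20%: 0.20 × 20 = 4.0 points; 0.20 × 40 = 8.0 points

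For a single subject in a row of m, f = 1/m and the shift is d/m:

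- m = 40: 20/40 = 0.5 point; 40/40 = 1.0 point
- m = 20: 20/20 = 1.0 point; 40/20 = 2.0 points

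The 8-point figure needs 8 therapy-related subjects in a row of 40 (8/40 = 20%) together with d = 40. It is an illustrative ceiling only.

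**Scale.** The exact (Clopper-Pearson) 95% interval for 30 responders out of 40 is 58.8% to 87.3%, a width of 87.3 − 58.8 = 28.5 points. The shift from one or two subjects in a row of 40 (0.5 to 2.0 points) is small beside that.

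**The case against.** The case for leaving the rule alone has several parts.

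- **No affected subject is shown.** Appendix 1 is a generic classification list and no evidence of enrolment: it also contains the promyelocytic subtype (M3), which the eligibility criteria bar. Protocol Section 4.3, exclusion criterion 4, further narrows the field. Apart from some low-risk cancers, it admits "any other cancer that has been in complete remission without treatment for" at least 5 years, and subjects on long-term adjuvant hormonal therapy at least 5 years after treatment of the primary tumor. This stands: the count may be small or zero. The criterion narrows the group without emptying it, and the synopsis names therapy-related AML as eligible.
- **The three-way wording is an eligibility line.** It is not repeated in the detailed inclusion criteria, and the protocol's efficacy analysis section defines no AML-type subgroup. So the SAP breaks no prespecified protocol analysis. That is true, but the label still disagrees with the protocol's own description of the disease.
- **The rule is disclosed and its effect can be undone.** SAP Section 5.3 tabulates the WHO subtypes, so the therapy-related count would be visible, and it adds: "By-subject listings of disease-specific and general medical history will be provided". SAP Section 6.1.2 adds: "Data listings for the clinical responses will be presented". A reader could regroup subjects from these. The analyses are descriptive and no decision rests on this subgroup. All of this limits the harm, but it does not correct the label on the summary tables.
- **A recode is only partial.** A therapy-related case recorded by FAB subtype alone would still be de novo. This stands, and only a footnote can deal with it unless disease history is used.

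**Conclusion.** The concern holds as a minor labelling error. As written, Section 3.4 would label any subject recorded under the therapy-related WHO subtype as de novo AML, contrary to the protocol's own categories. That reading rests on the text alone and is secure.

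The effect on results is conditional. It is zero if no subject has that subtype. Otherwise it is about 0.5 to 2.0 points per subject, for assumed de novo rows of 40 or 20 and an assumed response deficit of 20 to 40 points. A shift of that size would be unlikely to change a conclusion. It is confined to the AML-type subgroup tables and one baseline row. Overall remission rates, their confidence intervals, the Cohort C1A futility rule and the sample size do not depend on the label.

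**What to change.** In SAP Section 3.4, take the therapy-related WHO subtype out of the de novo default. Either give it its own level, which matches the protocol's three categories, or combine it with secondary AML under a label that says so, such as secondary/therapy-related AML. The documents do not prescribe either choice; both remove the wrong label. Use the same coding for the Section 5.2 baseline row.

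Add a footnote to both tables stating that subjects classified by FAB only are de novo by default, because the recode does not resolve them. If no subject has the therapy-related subtype, say so in that footnote.

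The cost is a one-line SAP edit and a recode of a subtype already on the Appendix 1 list. No new data are needed. SAP Section 1 provides that changes made after the SAP is final are documented in the clinical study report, so the correction can be made before or after that point.
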